#### **4.4 Subject Withdrawal Criteria**

A subject may withdraw from the study treatment or the study due to the following reasons:

1. Lost to follow up.
2. The subject withdraws consent.
3. Development of an imaging abnormality consistent with vasogenic edema, macrohemorrhage, or an area of superficial siderosis appears or a clinically symptomatic microhemorrhage.
4. Development of intolerable adverse event due to study treatment as determined by the investigator and/or subject.
5. Development of an intercurrent illness or condition for which the subject requires concomitant medications which are not allowed in the study.
6. Discovery that the subject entered the study in violation of the protocol or occurrence of a protocol violation during the study that may affect safety at the investigator's discretion.

7. Subject's pregnancy.
8. Subject's death.
9. The investigator feels that in the best interest of the subject's health, the subject is to be withdrawn from the trial.
10. Data not known before starting the trial become available and raise concern about the safety of the study drug such that continuation would pose potential risk to any particular subject.

### **The type and timing of the data to be collected and follow-up for withdrawn subjects**

When a subject decides to withdraw from the study treatment or the study, he/she should be contacted to obtain information about the reason(s) for discontinuation and any adverse events. For subjects who withdraw from the study treatment or the study after study drug administration, efforts will be made, as appropriate and at discretion of investigator, to have an early termination (ET) visit arranged as soon as possible. All study procedures listed in Visit 13/ET (see sections 8.2 and 8.3) should be completed at the early termination visit when applicable, including: ECG, physical examination, vital signs, clinical chemistry and hematology tests, serum anti-A $\beta$  antibody level evaluation, recordation of any AE/SAE, concomitant treatments (medications/therapy), imaging evaluations (18F-AV-45 PET and MRI), and neuropsychological tests (including MMSE, CDR-SB, ADAS-Cog, ADCS-ADL, and NPI). In addition, subjects will be encouraged to complete all remaining scheduled visits and procedures before the early termination visit.

If a subject is withdrawn at a scheduled study visit, the early termination visit could be conducted on the same day. Besides, in the event of a drop-out after study drug administration, all attempts should be made to follow-up the subject through telephone calls or by direct contact until the end of this study (Week 78), in order to document any delayed adverse drug reactions or adverse events.

## 5 TREATMENT OF SUBJECTS

### 5.1 Description of Study Drug

Study drug: UB-311 (UBITH® AD Immunotherapeutic Vaccine), 300 µg per 0.5 mL per vial.

Placebo: delivery vehicle without UB-311 active peptides and CpG.

### 5.2 Dosing Regimens and Rationale

Eligible subjects are randomly assigned in 1:1:1 ratio to one of the following treatments:

- Arm 1: UB-311 for a total of 7 intramuscular (IM) injections at Weeks 0, 4, 12, 24, 36, 48, and 60.
- Arm 2: UB-311 for a total of 5 IM injections at Weeks 0, 4, 12, 36, and 60. In order to maintain the blindness, subjects assigned to arm 2 will receive 2 IM injections of placebo at Weeks 24 and 48.
- Arm 3: placebo for a total of 7 IM injections at Weeks 0, 4, 12, 24, 36, 48, and 60.

Injections will be given on alternate arms or at different sites, which will be recorded.

The 300 µg of UB-311 in 0.5 mL sterile aqueous solution is the maximal concentration feasible in the current intramuscular injection formulation containing CpG-ODN and Adjuvphos. Therefore, the dose escalation in the Phase IIa study will be based on the cumulative doses according to various treatment schedules instead of different amount of UB-311 per injection.

A total of three injections of UB-311 at Weeks 0, 4, and 12 with a cumulative dose of 900 µg were evaluated in the Phase I clinical trial that showed acceptable safety, tolerability, immunogenicity, and positive clinical outcome in mild to moderate AD patients over a one-year period. In the Phase IIa study, the dose will be escalated based on increased number of injections than the Phase I study. Subjects assigned to Arm 1 will receive 7 injections of UB-311, 300 µg each at Weeks 0, 4, 12, 24, 36, 48, and 60 with a cumulative dose of 2,100 µg. Subjects assigned to Arm 2 will receive 5 injections of UB-311, 300 µg each at Weeks 0, 4, 12, 36, and 60 with a cumulative dose of 1,500 µg.

The Phase I study showed that three priming doses at Weeks 0, 4, and 12 successfully established sufficient immunogenicity against Aβ, thus the priming schedule was adopted for the current study. Additional doses for Arm 1 and Arm 2 at the frequency of 3 and 6 months, respectively, are intended to assess the requirement for maintaining elicited antibody levels. Furthermore, the dosing regimen of Arm 1 represents the most frequent injection schedule, allowing evaluation of safety and efficacy of the strongest antibody response.

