#### 6.1.1 Anti-A $\beta$ antibody measurement

For the immunogenicity assessment of the investigational product, UB-311, the level of anti-A $\beta$  antibodies in the serum samples will be measured by a validated enzyme immunoassay manufactured by United Biomedical, Inc. (UBI).

The level of anti-A $\beta$  antibodies is assessed at every visit throughout the study period from V1 to V13 (Weeks 0/baseline, 4, 12, 16, 24, 28, 36, 40, 48, 52, 60, 64, and 78). For visits that UB-311 or placebo is scheduled to be administrated (V1, V2, V3, V5, V7, V9, and V11), blood samples will be collected before the treatment.

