## 6.3.2 Efficacy assessment methods

### 6.3.2.1 Rating scales

All scales are rated by an independent clinical psychologist and/or study nurse who has to complete the training session specifically designed for this study.

MMSE and CDR/CDR-SB are evaluated at the first screening (S1), and at Weeks 24 (V5), 48 (V9) and 78 (V13). ADAS-Cog, ADCS-ADL, and NPI are evaluated at baseline (V1), and at Weeks 28 (V6), 52 (V10) and 78 (V13).

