5.9 Analysis of Immunogenicity Variable

Anti-A β antibodies will be summarized by presenting summary statistics of raw data and change from baseline values (n, mean, standard deviation, median, range) at each scheduled visit in mITT Population and PP Population.

The Kruskal-Wallis test or analysis of variance (ANOVA) for continuous variables for baseline information will be performed for comparing the un-adjusted change among Arm 1, Arm 2 and Arm 3.

A repeated-measures mixed-effects model with treatment (Arm 1+ Arm 2 vs. Arm 3, Arm 1 vs. Arm 3 and, Arm 2 vs. Arm 3), study visit, time-by-treatment, APOE4 status, and baseline as a

covariate will be used to analyze change from baseline of anti-A β antibodies. The unstructured covariance will be used in the modelling of the within-patient errors in the analysis. For APOE4 status subgroup analysis of MMRM, APOE4 factor will not be considered in the model. AUC of Anti-A β antibodies will be used an analysis of covariance (ANCOVA) model with treatment and baseline of Anti-A β antibodies as covariate. Antibody responders will be defined as the subjects with serum antibody titer > response threshold at any visit after baseline. The number and percentage of patients will be tabulated for each treatment group in mITT Population and PP Population at each post treatment scheduled visit. Treatment differences in the proportion antibody responders will be analyzed with the Chisq test. The one-sided 95% confidence interval (CI, right side) from all visits (V1 to V13) for subjects in Arm 3 (placebo group) will be calculated as the threshold of response.

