5.10 Analysis of Efficacy Data

Efficacy analyses will be performed on the mITT and PP populations. For change from baseline of ADAS-Cog total score, MMSE total score, ADCS-ADL total score, CDR-SB total score, NPI total score, A repeated-measures mixed-effects model with treatment (Arm 1 + Arm 2 vs. Arm 3, Arm 1 vs. Arm 3 and , Arm 2 vs. Arm 3), study visit, time-by-treatment, APOE4 status, and baseline as a covariate will be used to analyze change from baseline. The least square means using maximum likelihood estimate and its 95% will be provided. The unstructured covariance will be used in the modeling of the within-patient errors in the analysis.

For change from baseline of mean SUVR, A repeated- measures mixed-effects model with treatment (Arm 1 + Arm 2 vs. Arm 3, Arm 1 vs. Arm 3 and, Arm 2 vs. Arm 3), study visit, time-by-treatment, APOE4 status, and baseline as a covariate will be used to analyze change from baseline. The unstructured covariance will be used in the modeling of the within-patient errors in the analysis.

For change from baseline of mean SUVR by region, A repeated- measures mixed-effects model with treatment (Arm 1 + Arm 2 vs. Arm 3, Arm 1 vs. Arm 3 and, Arm 2 vs. Arm 3), study visit, time-by-treatment, and baseline as a covariate will be used to analyze change from baseline. The unstructured covariance will be used in the modeling of the within-patient errors in the analysis.

The p-values and confidence intervals for these efficacy endpoints were not adjusted for multiplicity, it should be used for screening purposes only, and that one side of 95% confidence intervals are provided to help gauge the precision of the estimates for treatment difference.

The proportion of PET positive subjects with visual read will be provided by number and percentage for each treatment group in mITT Population and PP Population at each post treatment scheduled visit. Treatment differences will be analysed with the Chisq test. The one-sided 95% confidence interval (CI, right side) between (Arm 1 + Arm 2 vs. Arm 3, Arm 1 vs. Arm 3 and, Arm 2 vs. Arm 3) from all visits will be calculated.

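### Arms 1 and 2 are treated identically until the Week 24 injection: through V5, rest inference on pooled UB-311 v placebo, and use the known equality in the later antibody analysis

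*Protocol*

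**What the plan says.** Protocol 5.2 sets out the two regimens: "Arm 1: UB-311 for a total of 7 intramuscular (IM) injections at Weeks 0, 4, 12, 24, 36, 48, and 60" and "Arm 2: UB-311 for a total of 5 IM injections at Weeks 0, 4, 12, 36, and 60". To keep the blind, "subjects assigned to arm 2 will receive 2 IM injections of placebo at Weeks 24 and 48". The same section says that the two boosting frequencies are there to learn how often injections are needed to maintain antibody levels.

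Antibody is measured at every visit from V1 to V13. At dosing visits "blood samples will be collected before the treatment" (Protocol 6.1.1). MMSE and CDR-SB are rated at screening and at Weeks 24, 48 and 78. ADAS-Cog, ADCS-ADL and NPI are first rated after baseline at Week 28. The first follow-up PET scan is at Week 52.

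SAP 5.9 analyses change in antibody with "A repeated-measures mixed-effects model with treatment (Arm 1+ Arm 2 vs. Arm 3, Arm 1 vs. Arm 3 and, Arm 2 vs. Arm 3", plus visit, time-by-treatment, APOE4 status and baseline, with unstructured covariance. SAP 5.10 uses the same contrasts for the scales and SUVR, with "study visit, time-by-treatment, APOE4 status, and baseline as a covariate will be used to analyze change from baseline" for the scales. Neither section limits the arm-specific contrasts to particular visits, and neither lists Arm 1 v Arm 2. SAP 5.9 also plans a Kruskal-Wallis test or ANOVA that "will be performed for comparing the un-adjusted change among Arm 1, Arm 2 and Arm 3", and tabulates responders by treatment group at each post-treatment visit.

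**The concern.** Until the Week 24 injection the two UB-311 arms are one treatment under two labels. Estimating each arm against placebo at those visits splits 30 subjects into two groups of 15 and produces two results whose true values are equal. If one arm is nominally significant at Week 16 and the other is not, a reader may take it for a regimen effect, because comparing regimens is the stated reason for having two.

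The second cost comes later. Since the arms are known to be equal at V2 to V5, any gap between them there is chance. The size of that gap helps to correct the later estimates, much as a baseline value does. The SAP model gives every arm its own mean at every visit and does not use this.

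**Working it through.** **1. Which data are shared.** Both arms have received 3 × 300 = 900 µg when Week 24 blood is drawn. The protocol's full-course totals reproduce: 7 × 300 = 2,100 µg and 5 × 300 = 1,500 µg.

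| Outcome | Post-baseline visits before the arms differ |
|---|---|
| Antibody | V2, V3, V4, V5 (Weeks 4, 12, 16, 24) |
| MMSE, CDR-SB | V5 only; no stated rule that rating precedes the injection |
| ADAS-Cog, ADCS-ADL, NPI | none |
| SUVR | none |

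The plan states no precision or power for any treatment contrast, so there is no figure of its own to reproduce. Below, n = 15 per arm with equal variances and complete data.

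**2. Early visits: standard error in SD units.** One arm v placebo: √(1/15 + 1/15) = 0.365. Pooled v placebo: √(1/30 + 1/15) = 0.316. Ratio 0.866, so the pooled standard error is 13% smaller.

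**3. Early visits: discordant verdicts.** The two arm-specific statistics share the placebo arm, so their correlation is (1/15)/(2/15) = 0.5. Simulated with 42-df t tests, two-sided 0.05:

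| True effect of UB-311 (SD, assumed) | Exactly one arm at p<0.05 |
|---|---|
| 0 | 8% |
| 0.3 | 16% |
| 0.5 | 26% |
| 0.8 | 32% |
| 1.0 | 24% |
| 1.5 | 3% |

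**4. Three-group test, if it is run at V2 to V5.** With means d, d, 0 the noncentrality is 15 × (2/3)d² = 10d². At d = 0.8 power is 58% (F, 2 and 42 df). The 30 v 15 t test has 70%.

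**5. Later antibody visits.** Let R² be the share of variance at a later visit explained by V2 to V5. Relative to the SAP model, constraining Arms 1 and 2 to be equal at V2 to V5 gives these standard error ratios:

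- Arm 1 v Arm 2: √[(1 − R²)k]
- One arm v placebo: √{[1.5 + 0.5(1 − R²)k]/2}
- Pooled v placebo: 1, no gain

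Here k = 1 if the regression coefficients are known, and k = 1 + 4/(42 − 4 − 1) = 1.108 if four are estimated. The documents give no correlations, so those below are assumptions. AR means decay per 12 weeks; Week 24 to Week 78 is 4.5 such periods, hence R² = r⁹.

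| Assumption | R² | Arm v placebo, k = 1 / 1.108 | Arm 1 v Arm 2, k = 1 / 1.108 |
|---|---|---|---|
| AR 0.8, Week 78 | 0.134 | 0.983 / 0.995 | 0.930 / 0.979 |
| AR 0.9, Week 78 | 0.387 | 0.950 / 0.959 | 0.783 / 0.824 |
| Compound symmetry 0.5 | 0.400 | 0.949 / 0.957 | 0.775 / 0.815 |
| Compound symmetry 0.8 | 0.753 | 0.901 / 0.905 | 0.497 / 0.523 |
| AR 0.9, Week 36 | 0.810 | 0.893 / 0.896 | 0.436 / 0.459 |
| No correlation | 0 | 1 / 1.013 | 1 / 1.053 |

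A simulation with estimated coefficients (20,000 runs) gave 0.962 and 0.818 at compound symmetry 0.5, and 1.013 and 1.051 at zero correlation, in line with the formula.

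These R² values are to be read as what remains after the baseline covariate. If compound symmetry of 0.5 to 0.8 describes raw values, the correlation after baseline is ρ/(1 + ρ) = 0.333 to 0.444, and R² = 4ρ²/(1 + 3ρ), taken at that correlation, is 0.222 to 0.339. With k = 1.108 the ratios become 0.983 to 0.966 and 0.928 to 0.856.

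**6. MMSE and CDR-SB, one shared visit.** By the same adjustment R² = 0.333² to 0.444² = 0.111 to 0.198. With k = 1 + 1/(42 − 1 − 1) = 1.025, arm v placebo gives 0.989 to 0.978, a gain of about 1 to 2%.

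**The case against.** The SAP already lists the pooled contrast. At the shared visits that is the efficient 30 v 15 estimate, and the constraint adds nothing to it. This stands: a reader might infer that the SAP overlooks pooling, and it does not.

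A reader might also infer that arm-specific results will certainly be reported from Week 4 for all outcomes. The documents do not say so. The SAP names no visits for its model contrasts, and its endpoints refer to the end of the study. The sentence on the three-group test mentions baseline information and no visit, so step 4 is conditional. Only antibody has shared visits from Week 4.

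Discordance may be small for antibody. The protocol reports a 100% Phase I response rate, so effects well above 1 SD are plausible once priming has taken hold, and at 1.5 SD discordance is 3%. The 8 to 32% range fits Week 24 MMSE and CDR-SB better, and the SAP already treats the p-values for those scales as screening only.

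The largest precision gain belongs to Arm 1 v Arm 2, which the SAP models do not list. For the contrasts that are listed the gain is modest and rests on assumed correlations. Unstructured covariance over 12 post-baseline visits has 12 × 13/2 = 78 parameters from about 45 subjects. With missing data the gain depends on how well these are estimated.

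What survives is narrower. Nothing in the SAP restricts the arm-specific contrasts to visits where the regimens differ, responders are tabulated by arm at V2 to V5, and an equality guaranteed by design goes unused.

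**Conclusion.** The point holds as an improvement in efficiency and interpretation. A reader might infer biased estimates or an inflated error rate, but separate arm means are valid, and each arm-specific test at an early visit keeps its nominal level.

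Through V5, differences between Arms 1 and 2 in antibody carry no information about regimen, apart from dosing deviations. The same holds in effect for Week 24 MMSE and CDR-SB, if the ratings precede the injection.

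From Week 36 to Week 78 the constraint reduces antibody standard errors by about 1 to 11% for arm v placebo and about 2 to 54% for Arm 1 v Arm 2. The gain is least at Week 78 if correlation decays with time. These figures assume equal variances and the correlations shown; if those are raw correlations, baseline adjustment takes up part of the gain. For MMSE and CDR-SB the arm v placebo gain is about 1 to 2% under compound symmetry.

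**What to change.** In SAP 5.9:

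- Constrain Arms 1 and 2 to a common mean at V2 to V5 in the antibody model (UB-311 v placebo through V5, three arms from V6).
- Through V5, base model contrasts, any unadjusted test and responder comparisons on UB-311 (n = 30) v placebo. Label by-arm figures at those visits as descriptive.
- From V6, keep the arm v placebo contrasts and add Arm 1 v Arm 2 for antibody, the comparison behind the two boosting intervals.

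In SAP 5.10, report only the pooled contrast for MMSE and CDR-SB at V5, and arm-specific contrasts from V9. The constraint at V5 is optional. First confirm that the Week 24 ratings are done before the injection.

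The cost is a few sentences and a recoded treatment-by-visit term, settled before unblinding, with no new data or patients. The statistical downside is small. If early and late visits were uncorrelated, the standard error would rise by about 1% (arm v placebo) or 5% (Arm 1 v Arm 2). The latter becomes about 6% if baseline and APOE4 use two more degrees of freedom: √(1 + 4/35) = 1.056.

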### 5.3 Handling of Study Drug

#### 5.3.1 Packing and Labelling

The treatment box for each subject includes 7 vials numbered in the order of injection. The boxes for Arm 1 contain 7 vials of UB-311. The boxes for Arm 2 contain 5 vials of UB-311 and 2 vials of placebo. The boxes for Arm 3 contain 7 vials of placebo. Each box and vial is labelled with the randomization code, storage condition, and manufacturer.

### 5.3.2 Storage

The study drugs have to be stored between 2°C and 8°C. The study drugs at each study site must be properly stored, under the responsibility of the investigator or the pharmacist in accordance with the storage conditions indicated on the label. The monitor should check the storage conditions during the monitoring visits.

## 5.4 Drug Accountability

The study drugs should be kept in pharmacy of each study site, and be administered to subjects in the clinical trial under the responsibility of the investigator. In addition, the investigator should keep accurate drug delivery records. Any study drug accidentally or deliberately destroyed should be accounted for and documented. Any discrepancies between the amounts dispensed and those returned should be explained.

After the end of the study, all used and unused vials of study drug should be packed, sealed, and returned to UNS. All remaining study drugs should be destroyed by UNS or its designee.

## 5.5 Concomitant Medicines

All concomitant medications should be recorded in the case report form (CRF).

### 5.5.1 Permitted Medicines

Permitted medicines/treatments are subject's routinely used medications or the treatments which are judged by the investigator as not to affect the efficacy and safety assessments in the study (e.g. antihypertensives).

In addition, the following medications may be permitted:

- Acetyl cholinesterase inhibitors (donepezil hydrochloride, rivastigmine tartrate, tacrine, galantamine); N-methyl-D-aspartate (NMDA) receptor antagonist (memantine); ergot alkaloids and their derivatives, must be on stable dose for at least 3 months prior to the screening visit and during the study period.
- Ginkgo biloba
- Piracetam (Nootropil)
- Vitamin E ( $\leq 400$  IU/day)

### 5.5.2 Prohibited Medicines

The following medications are prohibited within 4 weeks prior to the first screening visit (S1) and during the study period:

- Antiparkinson's drugs (e.g. L-dopa, dopamine agonists, amantadine)
- Neuroleptics, with the exception of haloperidol  $\leq 2$  mg/day, quetiapine  $\leq 300$  mg/day, risperidone  $\leq 2$  mg/day, sulpiride  $\leq 200$  mg/day, and olanzapine  $\leq 10$  mg/day
- Sedative/hypnotics (in exceptional cases where short-acting and intermediate-acting benzodiazepines are conditionally allowed, for example, midazolam in oral dosage  $\leq 7.5$  mg/day for sleep only, midazolam injection  $\leq 5$  mg/day for office procedures with sedation only, oxazolam  $\leq 10$  mg/day, alprazolam  $\leq 1$  mg/day, lorazepam  $\leq 1$  mg/day, bromazepam  $\leq 12$  mg/day with maximum starting dose of 1.5 mg, twice a day, estazolam  $\leq 1$  mg/day at bedtime for sleep only, and other hypnotics such as zolpidem  $\leq 10$  mg/day, and zopiclone  $\leq 7.5$  mg/day may be allowed during the study)
- Antidepressants (e.g. bupropion, imipramine, mirtazapine, nefazodone and trazodone) with the exception of selective serotonin reuptake inhibitors (SSRIs), e.g. fluoxetine, paroxetine, sertraline, fluvoxamine, escitalopram, citalopram and serotonin-norepinephrine reuptake inhibitors (SNRIs), e.g. venlafaxine, duloxetine, milnacipran, desvenlafaxine
- Heparin or thrombolytic therapy starting from 4-week screening period
- Other treatments, including traditional herbal medicines and nutritional supplements, that may disturb the study result at investigator's discretion

## **5.6 Subject Compliance**

The compliance to the study treatments will be checked by the investigator and recorded in the CRF.

## 6 ASSESSMENT OF INVESTIGATIONAL PRODUCT

### 6.1 Immunogenicity

Immunogenicity is evaluated as one of the primary endpoints in this study.

- Change from baseline in anti-A $\beta$  antibody levels through the end of the study (Week 78)
- Response rate (see section 6.1.2 for definition)

#### 6.1.1 Anti-A $\beta$ antibody measurement

For the immunogenicity assessment of the investigational product, UB-311, the level of anti-A $\beta$  antibodies in the serum samples will be measured by a validated enzyme immunoassay manufactured by United Biomedical, Inc. (UBI).

The level of anti-A $\beta$  antibodies is assessed at every visit throughout the study period from V1 to V13 (Weeks 0/baseline, 4, 12, 16, 24, 28, 36, 40, 48, 52, 60, 64, and 78). For visits that UB-311 or placebo is scheduled to be administrated (V1, V2, V3, V5, V7, V9, and V11), blood samples will be collected before the treatment.

